#### **A2. Aim 2 (proband and family interviews)**

To further assess participants' experiences of receiving the result of *KCNQ1* p.Thr224Met testing, the goal of this second, qualitative phase is to elaborate on the results of Aim 1 through semi-structured, in-depth in-person interviews. Interview participants (adults only) will be sampled purposively to include roughly 30 probands and 45 family members. In order to maximize variability with respect to the genetic test results (e.g., positive and negative), whether or not they shared their results, and primary implementation outcomes (e.g., whether or not they underwent cascade screening), we will enroll 15 probands who shared results with family members, 15 probands who did not share results, 15 family members who underwent cascade screening and were mutation positive, 15 family members who underwent cascade screening and were mutation negative, and 15 family members who did not undergo cascade screening. The goal of this sampling strategy was to achieve maximum variation and minimal informational redundancy. A guide for qualitative research is usually to include approximately 15 interviewees in order to obtain saturation and a homogeneous sample with maximum variation. Therefore, we expect to reach saturation and have a good representation of our participants.

### **B. Statistical methods with respect to each outcome**

#### **B1. Aim 1 (cascade screening intervention)**

##### **B1.1 Primary outcome**

Our primary outcome is the rate of uptake of cascade screening before ('traditional') versus after ('simplified') the intervention. Uptake for this outcome is defined as the proportion of first degree family members (i.e. offspring and siblings) of the initial 70 probands who undergo cascade screening out of all eligible first degree family members (as defined by the Fisher book). We will compare the proportion before versus after the simplified screening approaches. Any individuals who undergo screening before the intervention will no longer be eligible for screening with the simplified cascade screening so the

denominator will decrease accordingly. We have chosen to use the denominator of all first degree relatives defined by the Fisher book because this number is not dependent on participants returning the surveys where they will provide information on how many family members they told (and how many they have). Our secondary outcome includes the proportion of informed relatives who get screened. The number of participants screened for all outcomes will be obtained from charts (as [name] is ordering physician for all tests).

### **B1.2 Secondary outcomes**

- a. Extent of disclosure of genotype results before and after the intervention. This outcome is defined as the number of family members (siblings and children) told (reported via survey) out of the total number of proband first degree relatives (known from the Fisher Book and asked on the survey).
- b. Proportion of informed first-degree relatives who get screened before and after the intervention. This outcome is defined as the number of family members tested out of the number told by probands (reported via surveys)
- c. The overall rate of uptake of preventative therapy among probands and family members (e.g., see a cardiologist and/or take a beta-blockers)

Analyses of secondary outcomes (a) and (b) will occur in the same manner as the primary outcome, by comparing proportions before and after the intervention. For secondary outcome (c), we don't expect the proportion of appropriately treated carriers to be impacted by our intervention, but rather the absolute number of treated individuals would be impacted by detecting more carriers with improved cascade screening. For the disclosure outcome (a), we will compare results using the denominator based on Fisher book data and based on data reported in the survey. For the uptake of screening among those informed outcome (b), the denominator is based on the survey results (the proband will be asked who they disclosed results to and the family member will be asked if their family member told them). For the uptake of clinical recommendation outcome (c), we will use data from the participants' charts to determine whether beta-blocker therapy was indicated and prescribed. We will gather data from the survey on whether participants are following the recommendations. While we don't expect our intervention to change the proportion of individuals appropriately treated, we will compare the proportions before and after the intervention to confirm this assumption.

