## Study Procedures

**If you uploaded a separate research protocol document in the 'Research Protocol' page, cite the applicable section and page numbers from that document in the answer boxes below. (If this study is a collaborative UM/VA study please list each procedure that is being conducted and the locations where it is being conducted.)**

1 \* Describe all procedures being performed for research purposes only (these procedures would not be done if individuals were not in the study) and when they are performed, including procedures being performed to monitor subjects for safety or to minimize risks:

Individuals who participated in the KCNQ1 ROR study (probands) and their first degree blood-related family members will be invited to participate. All probands will be mailed an information / consent letter with a response form (uploaded in Informed Consent Section), a questionnaire about their attitudes and experience with genetic testing (uploaded to Surveys Section), and a sample family invitation letter (uploaded to Recruitment Section). In the consent letter, probands will be asked to complete and return the questionnaire as an indication that they agree to join the study. They will be informed that they may be asked to participate in an in-person interview. The letter will also ask if we can invite their adult first-degree family members who live locally to take part in the study, whether or not the proband participates. They will be given the option to enroll their minor children (with appropriate consent and assent) in the free cascade testing portion of the study. The proband will complete and return the response card to indicate whether they agree to contact of family members.

With the proband's permission, the family invitation letter will be mailed to the first-degree family members of the proband who live locally, using information from the 2009 Fisher Book and 2018 Address book of the Lancaster County Amish. At the proband's request, copies of the family invitation letter will, instead, be mailed to the proband so they can hand deliver them to family members of their choosing.

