## Surveys/Questionnaires

You indicated that this study involves surveys and/or questionnaires.

If you uploaded a separate research protocol document in the 'Research Protocol' page, cite the applicable section and page numbers from that document in the answer boxes below.

1 \* List all questionnaires/surveys to be used in the study, including both standardized and non-standardized assessments:

Baseline Proband questionnaire  
 Post-intervention Proband questionnaire  
 Post-intervention mutation negative Family Member questionnaire  
 Post-intervention mutation positive Family Member questionnaire  
 Family Member declined testing questionnaire  
 Medical, social, and family history questionnaire  
 Medication form

2 \* Upload a copy of all questionnaires/surveys:

Name	Created	Modified Date
 Family positive(0.03)	11/8/2018 1:53 PM	5/16/2022 11:33 AM
 Family negative(0.03)	11/8/2018 1:51 PM	5/16/2022 11:33 AM
 Family no testing(0.02)	2/3/2019 7:31 PM	5/16/2022 11:33 AM
 Medication Flow Sheet.docm(0.01)	2/4/2019 12:18 PM	2/4/2019 12:18 PM
 Medical, Social, and Family history form(0.01)	2/4/2019 12:17 PM	2/4/2019 12:17 PM
 Proband baseline(0.03)	9/13/2018 4:06 PM	2/3/2019 7:28 PM
 Proband followup(0.02)	11/8/2018 1:48 PM	2/3/2019 7:27 PM

3 \* What is the total length of time that each survey is expected to take?

20 minutes

4 \* Are any of the questions likely to cause discomfort in participants or cause harm if their confidentiality were breached? (i.e., Illegal activities)

Yes  No

5 \* Do any questions elicit information related to the potential for harm to self or others?

Yes  No

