### **B1.3 Missing data**

Based on the fact that our primary outcome data will come from tests ordered through [name], co-investigator, we expect very little missing data. For the secondary endpoints, we will rely on information obtained via surveys and will provide an incentive to encourage participants to complete the 2 surveys. In the case of missing data we will assess the types of missing data (random, random but not impacting dependent variables, or non-random). Our experience with the Amish suggests that once they commit to participate they will participate fully, so we do not anticipate a great deal of missing data. We have estimated that we will have an approximate 60% return rate of surveys based on previous data.

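### Secondary outcome (b) divides chart-counted tests from all families by survey-reported disclosures from about 60% of returns, with no rule that both counts come from the same families

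*Combined protocol and SAP*

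**What the plan says.** Outcome (b) stands in SAP B1.2 and, in the same words, in the protocol's Sample Size and Data Analysis, item 2. Its title describes screening among relatives who were informed. Its working definition is "This outcome is defined as the number of family members tested out of the number told by probands (reported via surveys".

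- **Numerator.** SAP B1.1: "The number of participants screened for all outcomes will be obtained from charts".
- **Denominator.** SAP B1.2 bases it on survey answers: "the proband will be asked who they disclosed results to and the family member will be asked if their family member told them". It gives no rule for combining the two reports.
- **Survey return.** SAP B1.3: "We have estimated that we will have an approximate 60% return rate of surveys based on previous data". This is one figure, not split by period or by type of respondent. The section says the type of missingness will be assessed but gives no handling rule.
- **Comparison.** Proportions before and after, as for the primary outcome.
- **Survey and contact are separate decisions.** In Study Procedures, item 1, "probands will be asked to complete and return the questionnaire as an indication that they agree to join the study". The same letter asks permission to invite adult first-degree relatives "who live locally to take part in the study, whether or not the proband participates".
- **Instruments.** Surveys/Questionnaires, item 1, lists a "Baseline Proband questionnaire" for the start. The family-member forms are the "Post-intervention mutation positive Family Member questionnaire", its mutation-negative counterpart, and a form for those who declined testing.

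**The concern.** The numerator is close to complete, because it comes from orders and charts. The denominator is only as complete as the returned surveys. The plan sees this hazard for the primary outcome: SAP B1.1 chooses the Fisher-book denominator because it does not rely on survey return. Outcome (b) has no such protection.

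Tests with no proband survey behind them can arise in two ways. Traditional-period tests sit in charts whether or not the proband later returns a form. After the intervention, a proband may permit contact with relatives and still not return the questionnaire. Minors add to the gap only in those same families, since a responding proband can report having told them.

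Outcome (b) is meant to separate more telling from more testing. If its value depends on how many forms come back, it cannot do that reliably. Two analysts could also report different numbers from the same data, one following the title and the other the definition.

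**Working it through.** **The plan's own figures.** SAP A1: 3% of 500 = 15 tested before; 500 − 15 = 485 remain; 18% of 485 = 87.3, so 87 after (87/485 = 17.9%). These reproduce. They belong to the primary outcome; no figure is given for (b).

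**Formula.** Let T be relatives tested (all in charts), D relatives truly told, and c the share of D captured by returned surveys. Assume every tested relative had been told. As defined, (b) = T/(cD) = (T/D)/c.

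**Level.** At 60% return, with non-responding probands having told similar numbers, and family-member reports recovering a share f of the missing disclosures, c = 0.6 + 0.4f.

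| f | c | Factor 1/c |
|---|---|---|
| 0 | 0.60 | 1.67 |
| 0.3 | 0.72 | 1.39 |
| 0.6 | 0.84 | 1.19 |

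If non-responders told k times as many relatives and nothing is recovered, the factor is (0.6 + 0.4k)/0.6: 1.33 at k = 0.5 and 2.33 at k = 2. Whenever true uptake among the informed exceeds c, (b) passes 100%.

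**Before/after difference.** Tests are the plan's 15 and 87. The numbers told are not in the documents; I assume 50 of 500 before and 194 of 485 after. True values are 15/50 = 30.0% and 87/194 = 44.8%: +14.8 points, ratio 1.49.

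| c before | c after | Before | After | Difference |
|---|---|---|---|---|
| 0.60 | 0.60 | 15/30 = 50.0% | 87/116.4 = 74.7% | +24.7 |
| 0.60 | 0.72 | 50.0% | 87/139.7 = 62.3% | +12.3 |
| 0.60 | 0.84 | 50.0% | 87/163.0 = 53.4% | +3.4 |
| 0.60 | 0.50 | 50.0% | 87/97 = 89.7% | +39.7 |

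In the first row the ratio is still 74.7/50.0 = 1.49.

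**No true change.** Hold the true value at 30% in both periods. With c of 0.60 then 0.84: 30/0.60 = 50.0% and 30/0.84 = 35.7%, a false fall of 14.3 points. With c of 0.60 then 0.50: 50.0% and 30/0.50 = 60.0%, a false rise of 10.0 points.

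**Outcome (a), Fisher-book version.** Here the mismatch is reversed: told relatives come from surveys, while the denominator covers all families if non-responders' relatives stay in it. At 60% return in both periods, and no family-member recovery, an assumed true rise from 25% to 40% reads 25 × 0.6 = 15% to 40 × 0.6 = 24%. Fifteen points read as 9.

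**The case against.** The title of (b) already implies that the tested are a subset of the informed, and a sensible analyst might match them. Relatives cannot be included without the proband's permission (Eligibility), and the questionnaire and response card travel in the same mailing, so after-period tests without a proband survey need a proband who returns the card alone. Family-member reports feed the denominator. For (a), the plan will compare both denominators, which would expose the dilution. This is a secondary outcome of a pilot that disclaims a formal comparison of uptake, and the 15% mark does not name (b).

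These points limit the size. They do not supply the missing rule: the stated definition and data sources still override the title.

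Three stronger readings are tempting, and the documents do not support them.

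- *That capture will differ by period.* Only a proband form is named as baseline, but the forms are not shown, and a later family questionnaire could ask about earlier disclosure. It is a possibility, and its direction is open.
- *That the share of tests falling in responding families alters the reading.* It does not. As defined, (b) counts all tests, so at equal capture of 0.60 the example reads +24.7 whatever that share is. The share matters only for how far (b) lies from a same-family ratio.
- *That minors are missed generally.* They complete no survey, but outcome (a) counts children among those told, so the gap is confined to families without a proband survey.

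**Conclusion.** The concern holds as a missing matching rule that makes (b) depend on survey capture. The absence of the rule is plain from the text. The inflation of 1/c follows directly from the definition: up to 1.67 at c = 0.60 if non-responders told similar numbers, and less with family-member recovery. With equal capture, the before/after ratio stays unbiased, but each level and the difference are inflated. That matters because the plan compares proportions, and its 3% to 18% example treats improvement as an absolute difference.

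That capture differs between periods is an inference held with medium confidence. If it does, the error can hide a gain or create one. The sizes rest on assumed numbers told, true proportions and capture, so they show scale and do not predict results. The primary outcome is untouched. The point should be fixed before analysis; it does not threaten the main result.

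**What to change.** In SAP B1.2 and the matching protocol text:

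1. For each period, take numerator and denominator of (b) from the same families: those whose proband returned that period's survey. Where the forms identify relatives, count as tested only those reported as told; otherwise match at family level.
2. Repeat (b) in families whose proband returned both surveys, so that a change in family mix does not drive the difference.
3. State one rule for using family-member reports of being told, applied alike in both periods. Show relatives from families without a proband survey as a separate line.
4. Limit the Fisher-book denominator of (a) to responding probands' relatives.
5. Report survey return by period beside (a) and (b), and give the before/after ratio with the difference.

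**Cost.** Wording and linkage. SAP B1.2 says probands are asked whom they told, while B1.1 speaks of how many, so individual linkage depends on the forms. Family-level matching needs only counts, but leaves tested relatives who were not told in the numerator. At 60% return, 0.6 × 88 ≈ 53 families remain (0.6 × 70 = 42 on the SAP's figure). If tests are evenly spread, about 0.4 × 87 ≈ 35 after-period and 0.4 × 15 = 6 before-period tests leave the numerator. Ignoring family clustering, the example's standard errors rise from √(0.30 × 0.70/50) = 6.5 to √(0.30 × 0.70/30) = 8.4 points before, and from √(0.448 × 0.552/194) = 3.6 to √(0.448 × 0.552/116.4) = 4.6 after. Selective non-response remains and should be acknowledged.

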Despite the very clear potential clinical benefit of screening family members of carriers to identify and counsel family members of carriers, uptake of cascade testing has traditionally been low, particularly in the United States where active screening (ie direct contact of relatives) is not allowed due to privacy laws. A study of hypertrophic cardiomyopathy found a 39% uptake of genetic counseling and testing among family members of a proband with a pathogenic mutation. Similar rates have been seen in breast cancer, and hereditary nonpolyposis colorectal cancer with update rates of 23-45%. As disease causing mutations are discovered more commonly, the investigation of the ELSI impact of this screening is paramount with greater numbers of individuals will requiring pharmacological treatment and having knowledge of their (or their children's) increased risk of sudden death. This question is particularly important with diseases with incomplete penetrance, such as LQTS. Identifying methods to increase the palatability of cascade screening within families is a high priority need.

We propose to conduct our study in the context of the Lancaster Amish, a population isolate. While there is a temptation to regard this as a limitation in terms of generalization to broader populations, this view fails to consider the magnitude of the problem in population isolates where deleterious actionable variants are most likely to be highly enriched, and frankly, where personalized medicine is most commonly practiced. We have identified 140 carriers of the KCNQ1 rs199472706 variant, and given the large family sizes of the Amish (7-8 offspring on average), this represents a huge additional pool of carriers who could potentially benefit from screening. In other words, there is a very large and disproportionate public health burden in isolate populations like the Amish (e.g., Ashkenazi, Mennonite, Hutterite, Sardinian, Icelandic, and Finnish, among others) for which population-specific screening interventions are sorely needed. As an aside, we certainly expect that lessons learned about cascade implementation in the Amish will be relevant to many other communities and populations, not just population isolates.

ID: V1EW4E02805EA0C00  
Name: v2\_Justification, Objective, & Research Design

HP-00081981

Supporting Literature\_V2

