## Retrospective Data

You indicated that the study involves the use of retrospective data.

1 \*What is the date range that the existing data was collected?

Beginning Date:

10/12/2015

End Date:

10/31/2018

2 \*What is the source of the data originally collected? (Check all that apply)

- Medical records
- Medical images
- Data collected under a different research study
- Commercial (for profit) entity
- Publicly available records
- Other

2.1 If Other, please specify:

2.2 If you checked "Data collected under a different research study", please provide the name of study, where the study was conducted, and the IRB number (if applicable).

HP-40375 Genome Wide Research for CVD Gene-Environment Interactions

HP-40367 Genetics of Longevity in the Amish

HP-40368 Amish Family Osteoporosis Study

HP-40370 Amish Family Diabetes Study

HP-43419 Pharmacogenomics of Anti-Platelet Intervention (PAPI) Study

HP-43451 The Amish Wellness Study

HP-52685 Brain Body Connection

HP-62972 Amish Exome Sequencing: Sitosterol Study

3 \*What specific data fields will you have access to/collect for the study? For example, name, initials, date of birth, Social Security number, income, demographic information, family units, housing, etc.

Probands who carry the KCNQ1 variant were identified through research testing and clinical confirmation testing performed under the above noted protocols. Their KCNQ1 variant status, name, address, and phone numbers are required to contact for study recruitment.

You can also upload a copy of the data fields/variables to be collected for the study:

Name	Created	Modified Date
------	---------	---------------

There are no items to display

ID: VIEW4E0E25AFA4000  
Name: v2\_Retrospective Data

HP-00081981

Prospective Data\_V2

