2. OASIS
3. Possible other large NIH databases (e.g. Database of Genotypes & Phenotypes (dbGaP), ClinVar)

2 \* What is the purpose of the registry/database?

1. The Amish Index Database is a relational database that contains a record of all individuals who have participated in research studies at the Amish Research Clinic in Lancaster PA under the direction of Drs. [name] and [name]. The database includes participant's name, date of birth, address, Fisher number, Fisher relationship, Subject ID numbers for each Amish study protocol that the individual has been enrolled in, and their NIH Anabaptist Genealogy Database (AGDB) number with related information to construct pedigrees. As part of the IRB-approved protocols, Amish research participants may provide consent to be recontacted for the opportunity to participate in future studies. The database is used to maintain current contact information for mailing out Amish Research Clinic newsletters and offering participants opportunities to participate in future studies and to construct pedigrees that are necessary for the genetic analyses associated with the research. The database is linked to study-specific genotype and phenotype data that can be used for primary and secondary analyses consistent with IRB approved consents.
2. OASIS (-Oomics Analysis, Search, and Information System) is a searchable database that includes genetic association results and is accessible by members of the Amish research group and their approved collaborators. Genetic analyses are pre-computed and the association results are loaded into the database. The database also contains limited amounts of individual level access to allow drawing of pedigrees and more detailed genetic results. However, users are never able to see individual level results.
3. Large public databases, for example: The database of Genotypes and Phenotypes (dbGaP) archives and distributes the results of studies that have investigated the interaction of genotype and phenotype. Such studies include genome-wide association studies, medical sequencing, molecular diagnostic assays, as well as association between genotype and non-clinical traits.

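### Outcome (b) divides relatives tested (charts) by relatives told (proband surveys) without linking the two sets, so it is not a proportion of informed relatives and the direction of its bias is unknown

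*Combined protocol and SAP*

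**What the plan says.** SAP B1.2 labels outcome (b) "Proportion of informed first-degree relatives who get screened before and after the intervention" and defines it so: "This outcome is defined as the number of family members tested out of the number told by probands (reported via surveys". The protocol's Sample Size and Data Analysis, item 2, repeats the definition.

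The two parts of the ratio have different sources:
- **Numerator.** SAP B1.1: "The number of participants screened for all outcomes will be obtained from charts". It does not depend on survey return, and a tested relative appears once.
- **Denominator.** SAP B1.2 bases it on surveys: "the proband will be asked who they disclosed results to and the family member will be asked if their family member told them". B1.1, however, describes the surveys as supplying the number of relatives told.
- **Completeness of the denominator.** SAP B1.3: "We have estimated that we will have an approximate 60% return rate of surveys based on previous data".

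For outcome (a), B1.2 plans two denominators, one from the Fisher book and one from the survey. Neither document states the counting unit for relatives linked to more than one proband, how the proband's and the relative's answers are combined, or that the tested must be a subset of the told.

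**The concern.** A proportion of informed relatives needs a numerator contained in its denominator, both counted in the same unit. Here one is a count of persons and the other may be a count of proband-relative reports.

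Shared relatives are plausible. Siblings and offspring are the relatives of interest, all probands carry the same variant in one community, and the protocol (Justification, Objective, & Research Design, item 4) writes "given the large family sizes of the Amish (7-8 offspring on average". Some probands may have come through family-based studies, since Retrospective Data, item 2.2, lists "HP-40370 Amish Family Diabetes Study" among the sources. A sibling told by three probands could add 3 to the denominator and at most 1 to the numerator.

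Non-return works the other way. If a proband's survey is missing, the relatives that proband told drop out of the denominator, while those who were tested stay in the numerator.

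At stake is whether (b) can show that informed relatives are more likely to be tested under simplified screening, which is one of the study's secondary questions.

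**Working it through.** **The plan's own figures.** The only numerical example concerns the primary outcome: 15/500 = 3.0% before; 500 − 15 = 485; 0.18 × 485 = 87.3, given as 87/485 after. Also 15/7 = 2.1 and 87/7 = 12.4 probands. These reproduce. No figure is given for (b).

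**Inputs.** From the documents: 15/500, 87/485 and 60% survey return. Assumed, because the documents are silent: the share *s* of relatives with *k* probands (the rest have one), the probability *q* that each linked proband tells a relative (independently), and that every tested relative was told by a proband.

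**Step 1: effect of summing reports, full return.** A relative with *k* probands gives *kq* expected reports but is told with probability 1 − (1 − q)^k. Factor on (b) = [1 − (1 − q)^k]/(kq).

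| | q = 0.3 | q = 0.5 | q = 0.7 |
|---|---|---|---|
| k = 2 | 0.85 | 0.75 | 0.65 |
| k = 3 | 0.73 | 0.58 | 0.46 |

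With no shared relatives the factor is 1.

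**Step 2: one scenario (s = 30%, k = 2, q rising from 0.3 to 0.6).**
- Persons told per relative: 0.7 × 0.3 + 0.3 × 0.51 = 0.363 before; 0.7 × 0.6 + 0.3 × 0.84 = 0.672 after.
- Reports per relative: 0.7 × 0.3 + 0.3 × 0.6 = 0.390 before; 0.7 × 0.6 + 0.3 × 1.2 = 0.780 after.
- (b) by persons: 15/(500 × 0.363) = 8.3%; 87/(485 × 0.672) = 26.7%; change 18.4 points.
- (b) by reports: 15/(500 × 0.390) = 7.7%; 87/(485 × 0.780) = 23.0%; change 15.3 points.

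Over s = 10% to 50%, k = 2 or 3, and q rising from 0.3 to 0.6 or from 0.5 to 0.8, summing reports multiplies (b) by 0.69 to 0.97 before and 0.56 to 0.95 after.

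**Step 3: does the distortion differ between periods?** Only if telling changes. At s = 30%, k = 2:
- q = 0.5 in both periods: 0.575/0.650 = 0.885 both times.
- q falling from 0.6 to 0.3: 0.86 before and 0.93 after, so the larger deflation comes first.

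**Step 4: add 60% return, chart numerator unchanged.**
- No overlap: (b) is multiplied by 1/0.6 = 1.67.
- Step 2 scenario: 15/(0.6 × 195) = 12.8% and 87/(0.6 × 378.3) = 38.3%; change 25.5 points. The true values are 8.3% and 26.7%, so the reported figures are now too high.
- Share of relatives that must be shared for the two errors to cancel: k = 2 with q = 0.8, all of them; k = 3 with q = 0.8, 42%; k = 3 with q = 0.5, 89%; at q = 0.3, no share suffices for k = 2 or 3.

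**Step 5: is de-duplication alone enough?** No. In the same scenario at 60% return, distinct persons reported as told number 500 × [0.7 × 0.18 + 0.3 × (1 − 0.82²)] = 112.1 before and 485 × [0.7 × 0.36 + 0.3 × (1 − 0.64²)] = 208.1 after. Then (b) = 15/112.1 = 13.4% and 87/208.1 = 41.8%, further from the truth than in Step 4. The numerator has to be restricted to the told set as well.

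**The case against.** The strongest reply is that the plan never says reports are summed. The label speaks of informed relatives, probands are asked whom they told, and relatives are asked too, so distinct persons could be counted. That stands: double counting is a possible execution, not a stated rule. But B1.1 also describes the surveys as giving a number told, and no rule decides between the two readings. Nor does this reply touch the mismatch from non-return.

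Three stronger inferences are tempting, and the documents do not support them:
- **That (b) is biased downward.** Step 4 shows that the 60% return usually outweighs double counting.
- **That the downward pull is greater after the intervention.** This needs telling by several probands to rise. The protocol poses more telling as a question and gives no rate for either period.
- **That the amount of overlap can be read from the family counts.** With 7.5 children and 6.5 siblings per proband (14 relatives), 88 × 14/700 = 1.76, but the SAP's 70 probands give 70 × 14/700 = 1.40. Both ratios assume that the 700 are distinct persons and that families are complete. At 700/88 = 8.0 or 700/70 = 10.0 relatives per proband, smaller families with no sharing fit as well. Study titles do not establish kinship among probands either. Dividing (b) by such a ratio would further require every linked proband to tell everyone and to return the survey.

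Outcome (a) is also partly protected: its survey-denominator version sets reports against reports. Finally, (b) is a secondary outcome in a pilot that disclaims a formal before/after comparison, which limits the severity but does not make the ratio interpretable.

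**Conclusion.** The point holds as a defect of definition. As written, (b) sets a complete count of persons against an incomplete survey count of unspecified unit, so it does not validly estimate the proportion of informed relatives who are tested. Two errors act in opposite directions: a factor of 0.85 to 0.65 for a relative with two probands at telling rates of 0.3 to 0.7, and up to 1.67 from 60% return. Their sizes rest on overlap and telling rates that the documents do not give, and on independent telling, so the net direction is unknown. The before/after change is affected as well: in the worked scenario a true 18.4 points reads as 15.3 with full return and 25.5 with 60% return. Outcome (a) has the unit mismatch only in its Fisher-book version. The primary outcome does not use the surveys; for it, the open question is whether its denominators count distinct persons.

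**What to change.** Amend SAP B1.2 and the protocol's Sample Size and Data Analysis, item 2, as follows:
- Count each relative once, keyed by Fisher or genealogy number.
- Define told as named by at least one proband with a returned survey, and state how the relative's own answer is used (for example, as a sensitivity check).
- Count as tested in (b) only members of that told set who have a chart test.
- Use distinct persons for the Fisher-based denominators of (a) and of the primary outcome.
- State whether 700, 500 and 485 are distinct persons, and reconcile the 70 and 88 probands to which the same 700 is attached.

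The cost is wording and record linkage. For research participants the identifiers are already held (Data Registry, item 2): "The database includes participant's name, date of birth, address, Fisher number, Fisher relationship". The Fisher book already supplies the denominators, and probands are asked whom they told. The questionnaires are not among the documents; if they record only a count, names would also have to be collected. Matching removes the arithmetic mismatch. It does not remove selection if probands who return surveys differ from those who do not, so the return rate should be reported beside (b) for each period.
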